Appendix B. Immune-Related Response Criteria

The immune related response criteria* (irRC) has been developed to adequately characterize additional patterns of response and progression specific to patients treated with immunotherapy, that cannot be captured by the conventional criteria such as such as Response Evaluation Criteria in Solid Tumors (RECIST).

Antitumor response based on total measurable tumor burden.

For the irRC, only index and measurable new lesions are taken into account (in contrast to conventional WHO criteria, which do not require the measurement of new lesions, nor do they include new lesion measurements in the characterization of evolving tumor burden). At the baseline tumor assessment, the sum of the products of the two largest perpendicular diameters (SPD) of all index lesions (five lesions per organ, up to 10 visceral lesions and five cutaneous index lesions) is calculated. At each subsequent tumor assessment, the SPD of the index lesions and of new, measurable lesions ($\geq 5 \times 5$ mm; up to 5 new lesions per organ: 5 new cutaneous lesions and 10 visceral lesions) are added together to provide the total tumor burden:

$$\text{Tumor Burden} = \text{SPD}_{\text{index lesions}} + \text{SPD}_{\text{new, measurable lesions}}$$

Time-point response assessment using irRC.

Percentage changes in tumor burden per assessment time point describe the size and growth kinetics of both conventional and new, measurable lesions as they appear. At each tumor assessment, the response in index and new, measurable lesions is defined based on the change in tumor burden (after ruling out irPD). Decreases in tumor burden must be assessed relative to baseline measurements (i.e., the SPD of all index lesions at screening).

Overall response using the irRC.

The overall response according to the irRC is derived from time-point response assessments (based on tumor burden) as follows:

- irCR, complete disappearance of all lesions (whether measurable or not, and no new lesions)
 - confirmation by a repeat, consecutive assessment no less than 4 wk from the date first documented
- irPR, decrease in tumor burden $\geq 50\%$ relative to baseline
 - confirmed by a consecutive assessment at least 4 wk after first documentation
- irSD, not meeting criteria for irCR or irPR, in absence of irPD
- irPD, increase in tumor burden $\geq 25\%$ relative to nadir (minimum recorded tumor burden)
 - confirmation by a repeat, consecutive assessment no less than 4 wk from the date first documented

Appendix C. ECOG Performance Status

The ECOG Scale of Performance Status, developed by the Eastern Cooperative Oncology Group, [name], Group Chair*, describes a patient's level of functioning in terms of their ability to care for themselves, daily activity, and physical ability (walking, working, etc.).

Grade	Description
0	Normal activity. Fully active, able to carry on all pre-disease performance without restriction.
1	Symptoms, but ambulatory. Restricted in physically strenuous activity, but ambulatory and able to carry out work of a light or sedentary nature (e.g., light housework, office work).
2	In bed <50% of the time. Ambulatory and capable of all self-care, but unable to carry out any work activities. Up and about more than 50% of waking hours.
3	In bed >50% of the time. Capable of only limited self-care, confined to bed or chair more than 50% of waking hours.
4	100% bedridden. Completely disabled. Cannot carry on any self-care. Totally confined to bed or chair.
5	Dead.

Appendix D. Study Calendar

Study Procedures	Screening Period ¹	Treatment Period ²			Follow-up Period ³	
	Days -28 to -1	Day 1 ²⁵	Weekly C1 Only	Every 3 cycles (+/-1 week) ²¹	30 (±7) Days ²²	Long Term
Informed Consent	X ⁴					
Demographics	X					
Medical and Cancer History	X					
Concomitant Medications	X		X --- (throughout study ⁵) --- X			
Physical Examination	X	X	X		X	
Height	X					
Vital Signs and Weight⁶	X	X	X		X	
ECOG Performance Status⁷	X	X	X		X	
CBC with Differential	X ⁸	X ¹⁰	X		X	
Chemistries including LFTs	X ⁸	X ¹⁰	X		X	
Thyroid Function Tests	X			X	X	
Serum Pregnancy Test⁹	X ^{8, 9}	X ²⁶		X ⁹	X ⁹	
Pembrolizumab		X ¹¹				
Oxaliplatin		X ¹²				
Capecitabine		X ¹³				
Adverse Event Assessment	X	X --- (throughout study ⁵) --- X				
Tumor Assessment¹⁴	X			X		X ²³
Blood Tumor Markers¹⁵	X			X		X ²³
Archived Tumor Tissue¹⁶	X ¹⁶					X ¹⁶
Tumor Biopsy¹⁷	X ¹⁷		X ¹⁷			
PBMC¹⁸	X ¹⁸			X ¹⁸	X ¹⁸	X ²⁷
Plasma¹⁹	X ¹⁹			X ¹⁹	X ¹⁹	X ²⁷
Whole Blood²⁰	X ²⁰					
Survival						X ²⁴

- Refer to [Section 5.1](#).
- Refer to [Section 5.2](#). Cycle length is 21 days. However, for dose expansion cohort, the first cycle (ie. biomarker cycle) is 28 days in length and subsequent cycles are 21 days in length. Visits for each cycle are Day 1 except for Cycle 1 when visits are weekly (ie. C1D8, C1D15 and for dose expansion cohort only, C1D22) and as clinically indicated.
- Refer to [Section 5.3](#).
- May be completed more than 28 days prior to Cycle 1 Day 1.
- Document this data throughout study when changes or events occur.
- Obtain temperature (°C), blood pressure, heart rate, and weight (kg).
- At screening, obtain within 7 days to first dose of study treatment. Refer to [Appendix C](#).
- Must perform within 7 days prior to Cycle 1 Day 1. If completed within 7 days of Cycle 1 Day 1, no need to repeat. If repeated on Cycle 1 Day 1, must wait for results to confirm eligibility prior to starting study drug.
- Only for women of childbearing potential.
- After Cycle 1, may perform up to 3 days prior to Day 1.
- Pembrolizumab (see [Section 6.2](#)) is administered on Day 1 of each cycle.
- Oxaliplatin (see [Section 6.3](#)) is administered on Day 1 of each cycle except for first cycle (ie. biomarker) cycle of dose expansion cohort only when administered on Day 8 (ie. pembrolizumab monotherapy lead-in period).
- Capecitabine (see [Section 6.4](#)) is taken on Days 1-14 of each cycle except for first cycle (ie. biomarker) cycle of dose expansion cohort only when taken on Days 8-22 (ie. pembrolizumab monotherapy lead-in period).
- Radiographic assessments (ie. restaging scans) include CT and/or MRI of chest, abdomen and pelvis after every 3 cycles (9 weeks). Same method for tumor assessment should be employed at every assessment.
- If clinically indicated (ex. CEA and/or CA19-9).
- If FFPE tumor tissue is available, refer to [Section 8.1](#) and Study Manual.

17. For patients accrued to the dose expansion cohort with tumor lesion that is amenable to safe biopsy, pre-treatment (up to 1 week prior to pembrolizumab monotherapy lead-in) and on-treatment (C1 D7 or D8, prior to oxaliplatin and capecitabine/end of one week pembrolizumab monotherapy lead-in in Cycle 1) tumor biopsies will be performed in the first cycle (ie. biomarker cycle). Refer to [Section 8.1](#) and Study Manual.
18. Peripheral blood collection for PBMCs (see [Section 8.2](#) and Study Manual) at the following time points: baseline (may be obtained on Cycle 1 Day 1 prior to the first dose of study drug); end of monotherapy lead-in on Day 8 (biomarker cycle of dose expansion cohort only), end of first cycle of combination therapy on Day 29 (biomarker cycle of dose expansion cohort only), first restaging only (ie. after Cycle 3), and disease progression or treatment discontinuation. Note – There is no PBMC collection at 30-day off treatment follow-up.
19. Peripheral blood collection for plasma (see [Section 8.3](#) and Study Manual) at the following time points: baseline (may be obtained on Cycle 1 Day 1 prior to the first dose of study drug); end of monotherapy lead-in on Day 8 (biomarker cycle of dose expansion cohort only), end of first cycle of combination therapy on Day 29 (biomarker cycle of dose expansion cohort only), each restaging, disease progression or treatment discontinuation and 30-day off treatment follow-up.
20. Peripheral blood collection for whole blood (see [Section 8.4](#) and Study Manual at the following time point: baseline (may be obtained on Cycle 1 Day 1 prior to the first dose of study drug).
21. After every 3 cycles.
22. After the last dose of study drug.
23. Subjects discontinued from study treatment with no documented disease progression and no subsequent anti-cancer treatment should have disease status and blood tumor markers (if clinically indicated) followed per standard of care schedule until disease progression or start of new anti-cancer treatment regimen is documented. Disease status may be collected by personal interviews or review of medical records.
24. Subjects are followed for survival up to 3 years after the last subject starts the study drug regimen or until the study is closed (whichever comes first). Survival status may be collected by personal interviews or review of medical or public records.
25. Treatment visits may occur within +/-3 days of D1 for C2 and all subsequent cycles.
26. Cycle 1 day 1 only. After that, will redo at restaging visits.
27. Only for subjects who achieved a complete response and have consented to the additional collection.

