3.0 STUDY DESIGN

3.1 Study Description

This is a single arm, phase II study to assess the safety, tolerability, and efficacy of the recommended phase II dose (RPTD) of the combination of pembrolizumab, oxaliplatin and capecitabine in patients with previously untreated metastatic esophagogastric adenocarcinoma. The study will be conducted in two stages: 1) safety validation and 2) dose expansion. Approximately 50 subjects may be accrued to ensure the trial obtains 5 evaluable subjects in the safety validation cohort and 30 evaluable subjects in the dose expansion cohort. Patients will be enrolled at the Duke Cancer Institute and select external collaborating institutions (dose expansion cohort only).

- Enrolled subjects are defined as subjects who give informed consent.
- Screen failures are defined as subjects who give informed consent and do not meet eligibility criteria.
- Accrued subjects are defined as subjects who give informed consent and meet eligibility criteria.
 - Withdrawal: Subject accrued but later withdrawn from the study, either before or after receiving a study drug.
 - Evaluable: In the Safety Validation Cohort, subjects who are accrued, received study treatment, and completed the first cycle of safety assessments or have dose limiting toxicity (DLT) which is study treatment related that precludes completing the full cycle of assessments will be considered evaluable for DLT. All subjects (in Safety Validation and Dose Expansion) who are accrued and receive any study treatment will be considered evaluable for toxicity. All subjects in Safety Validation and Dose Expansion who are accrued and receive any study treatment will be considered evaluable for efficacy.
 - Non-evaluable: In the Safety Validation Cohort, subjects who accrued but did not complete the first cycle of safety assessments due to reasons other than study treatment-related toxicity (e.g. disease progression or inter-current illness) are considered non-evaluable for DLT.

Table 3.1 Cohorts

Cohort	No. Evaluable Subjects	Oxaliplatin mg/m ² IV, Day 1 every 21 days*	Capecitabine mg/m ² PO, BID Days 1-14 every 21 days*	Pembrolizumab mg IV, Day 1 every 21 days*
Safety Validation	5	130	850 or 1000**	200
Dose Expansion	30	130	850 or 1000**	200

*For dose expansion cohort, Cycle 1, biomarker cycle, is 28 days in length. Cycles 2 and beyond are 21 days.

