5.2 Treatment Period

During the Treatment Period, subjects will receive pembrolizumab and oxaliplatin on Day 1 and capecitabine on Days 1-14 of each 21-day cycle until either: 1) disease progression; 2) the occurrence of unacceptable treatment-related toxicity; or 3) other reason(s) for subject discontinuation as described in [Section 5.7](#). Toxicity-related dose modifications of pembrolizumab, capecitabine and oxaliplatin may occur during the Treatment Period. Dose modification guidelines are described in [Section 7.1](#).

NOTE: For the dose expansion cohort only, the first cycle (i.e. biomarker cycle) will be modified to allow assessment of biomarkers related to pembrolizumab; the length will be 28 days. Patients will receive pembrolizumab monotherapy on Cycle 1 Day 1. Treatment with oxaliplatin and capecitabine will begin on Cycle 1 Day 8; capecitabine will be dosed for 14 days (ie. Days 8-21), followed by one week off drug (ie. Days 22-28). Cycle 2 will start on Day 29 of study (ie. 28 days after pembrolizumab monotherapy and 20 days after start of capecitabine and oxaliplatin). For cycles 2 and beyond, the cycle length is 21 days. A treatment window of +/- 3 days is allowed for day 1 of cycle 2 and all subsequent cycles.

All subjects will have study procedures weekly during the first cycle, then Day 1 of each cycle. After the completion of the first cycle, laboratory assessments may be obtained up to 3 days prior to treatment. If necessary, the treatment visit may be within +/- 3 days of the scheduled day 1 for cycle 2 and all subsequent cycles. If clinically indicated, additional visits and/or safety assessments may be warranted.

The following study procedures must be completed on **Day 1 of each cycle**:

- Physical examination
- Vital signs and weight
- Concomitant medications
- ECOG performance status
- Adverse event assessment
- CBC with differential
- Chemistries including LFTs

The following study procedures must be completed on **weekly in Cycle 1 only**:

- Physical examination
- Vital signs and weight
- Concomitant medications
- ECOG performance status
- Adverse event assessment
- CBC with differential
- Chemistries including LFTs

For **dose expansion cohort only**, the following study procedures must be completed **pre-dose on Cycle 1 Day 8**:

- PBMC
- Plasma
- Tumor biopsy (Can be performed on Day 7 if needed. Only applicable to patients in dose expansion that have lesions amenable to safe biopsy)

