6.4.2 Administration

At the discretion of the treating physician, the patient may receive 850mg/m² or 1000mg/m² of capecitabine. Capecitabine will be administered at a dose of 850/1000 mg/m² twice daily, for a total daily dose of 1700/2000 mg/m² beginning the morning of Day 1 of each 3-week cycle and continuing through the evening of Day 14; except in the "biomarker cycle" (i.e. first cycle for subjects in the dose expansion cohort). During the biomarker cycle, capecitabine will begin on Day 8 (to allow for one week of pembrolizumab monotherapy for biomarkers). A treatment window of +/- 3 days of day 1 is allowed for cycle 2 and all subsequent cycles.

See current capecitabine package insert for dosing instructions in patients with moderate renal impairment.

The dose of capecitabine will be calculated on the basis of milligrams of drug per square meter (mg/m²) of body surface area (BSA). The dose of capecitabine will be rounded to the nearest dose that can be obtained by using the 500 mg tablets. Since capecitabine tablets cannot be split, patients may take different numbers of pills in the morning and evening in order to achieve the appropriate dose. The following is an example of how dose rounding may be performed:

Explanation: $[\{BSA\} m^2 \times \{dose level\} mg/m^2] \times 2 = \text{Daily Dose mg}$
Daily Dose mg $\div 500$ mg tablet = number of tablets per day, rounded to whole tablets
Divide number of whole tablets per day into 2 doses for morning (AM) and evening (PM)

Calculation: $[1.68m^2 \times 1000mg/m^2] \times 2 = 3360mg$
 $3360mg \div 500mg$ tablet = 6.72 tablets per day, rounded to 7 tablets per day
Divide 7 tablets into 2 doses = three 500mg tablets in AM and four 500mg tablets in PM

The dose will be recalculated per institutional standard (e.g., based on the new body surface area prior to the start of each cycle only if the weight changes by 10% from baseline).

Capecitabine will be taken orally. The total daily dose should be taken as two divided doses approximately 12 hours apart, within 30 minutes after the ingestion of food, ideally after breakfast and the evening meal. Tablets should be swallowed with approximately 200 ml of water (not fruit juices). Tablets are not scored and should not be split. If needed, capecitabine may be dissolved for administration either orally or via G or J tube but patient must receive safety handling training from pharmacy personnel.

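### Study calendar footnote 13 runs biomarker-cycle capecitabine to Day 22; the synopsis and Section 5.2 stop it on Day 21

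*Combined protocol and SAP*

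**What the plan says.** Four places in the combined protocol and SAP bear on how long capecitabine is taken in Cycle 1 of the dose expansion cohort (the biomarker cycle).

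- **Appendix D, footnote 13.** Capecitabine is taken on Days 1-14 of each cycle, except in the first cycle of the "dose expansion cohort only when taken on Days 8-22". The footnote refers the reader to Section 6.4.
- **Section 5.2, with the same wording in the synopsis (Study Drug Regimen).** In that cycle "capecitabine will be dosed for 14 days (ie. Days 8-21), followed by one week off drug (ie. Days 22-28").
- **Section 6.4.2.** In a regular cycle dosing is twice daily, "beginning the morning of Day 1 of each 3-week cycle and continuing through the evening of Day 14". The biomarker cycle is then excepted: "During the biomarker cycle, capecitabine will begin on Day 8 (to allow for one week of pembrolizumab monotherapy for biomarkers"). No end day is given for it.
- **Section 3.1, note to Table 3.1.** "For dose expansion cohort, Cycle 1, biomarker cycle, is 28 days in length"; later cycles last 21 days. The table itself schedules capecitabine for 14 days per cycle.

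**The concern.** The footnote and Section 5.2 describe the same drug, cohort and cycle, and they disagree about Day 22. The footnote makes it a dosing day; Section 5.2 and the synopsis make it the first day of rest.

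Section 5.0 sends readers to Appendix D for the schedule, and the expansion cohort is open at external sites as well as the lead site. Someone who checks the footnote against its own cross-reference finds only a start day in Section 6.4.2, so the error is not caught there. Two things are at stake: up to one extra day of a cytotoxic drug, and doubt over whether a Day 22 dose counts as a protocol deviation under Section 11.3.

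**Working it through.** **Inputs**

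- Dosing days in Section 5.2 and the synopsis: 8 to 21. Rest days: 22 to 28.
- Dosing days in Appendix D, footnote 13: 8 to 22.
- Two doses per day of 850 or 1000 mg/m² each (Section 6.4.2).
- Biomarker cycle length: 28 days (Section 3.1).

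The day count is inclusive: last day − first day + 1.

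**The plan's own figure**

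- Dosing: 21 − 8 + 1 = 14 days, as Section 5.2 states, and 14 × 2 = 28 doses.
- Rest: 28 − 22 + 1 = 7 days, the stated week.
- Whole cycle: 7 lead-in days (Days 1-7) + 14 + 7 = 28 days, the stated length.

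Section 5.2 is therefore consistent with itself and with Section 3.1.

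**The footnote as written**

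- Dosing: 22 − 8 + 1 = 15 days.
- Rest left in a 28-day cycle: Days 23-28, which is 6 days.
- If the footnote's dosing days and Section 5.2's rest days both applied, the cycle would last 7 + 15 + 7 = 29 days, one too many.

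**Number of doses under Days 8-22**

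| First and last dose | Doses | Excess over 28 |
|---|---|---|
| Morning Day 8 to evening Day 22 | 15 × 2 = 30 | 2 (30/28 = 1.071, or 7.1%) |
| One half-day fewer at either end | 29 | 1 (3.6%) |
| Evening Day 8 to morning Day 22 | 1 + 13 × 2 + 1 = 28 | 0 |

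**Cycle total at the upper bound**

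- At 850 mg/m²: 28 × 850 = 23,800 against 30 × 850 = 25,500 mg/m², a difference of 1,700 mg/m².
- At 1000 mg/m²: 28 × 1000 = 28,000 against 30 × 1000 = 30,000 mg/m², a difference of 2,000 mg/m².

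**Which figure is wrong**

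Section 5.2 gives a duration, the dosing days and the rest days, and all three agree. Table 3.1, Section 6.4.2 and the footnote itself use 14 dosing days for regular cycles. Only Days 8-22 departs from that pattern.

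**The case against.** The strongest reply is that the footnote may imply no extra drug. Section 6.4.2 states its morning-to-evening convention for regular cycles and then excepts the biomarker cycle, so a morning start on Day 8 is not laid down. Day 8 also carries pre-dose blood draws, in some patients a biopsy, and a two-hour oxaliplatin infusion. A first capecitabine dose that evening is plausible, although no clock time is given, and 28 doses would then end on the morning of Day 22. This stands as the lower bound on the effect. It does not reconcile the texts, because Section 5.2 and the synopsis both place Day 22 in the rest period.

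Other points on that side:

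- **Corroboration.** The synopsis and Section 5.2 share one sentence, so they are not two independent sources. The sentence after it also miscounts, giving 20 days from the start of chemotherapy on Day 8 to Day 29 when 29 − 8 = 21. Both remarks are fair. The case for 14 days does not need the repetition: it rests on the 28-day sum and on the regular-cycle schedule. Every version starts capecitabine on Day 8, so the second slip does not support Day 22.
- **Size.** The physician may already choose 850 or 1000 mg/m², a step of 1000/850 − 1 = 17.6%. Tablet rounding in the protocol's own example moves 3,360 mg to 3,500 mg, or 4.2%. An upper bound of 7.1% in one cycle is modest beside these. That supports a minor rating; it does not make the footnote right.
- **Timing.** This is Version 9.0, dated 2022, of a protocol first dated 2017, with 12 months of planned enrolment. The documents do not say whether any patient still had the biomarker cycle ahead. If none had, the correction mainly serves the record and the judging of past dosing.

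**Conclusion.** The concern holds. Footnote 13 of Appendix D is wrong as written and should read Days 8-21.

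The effect is confined to one cycle of the dose expansion cohort: between 0 and 2 extra doses and, on a literal reading, 6 rest days instead of 7. The upper bound assumes that a site follows the footnote literally, with both doses on Day 8 and both on Day 22. Nothing in the documents shows that any patient was dosed on Day 22.

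No statistical quantity changes. Dose-limiting toxicity is judged in the five safety validation patients, who take capecitabine on Days 1-14, and neither the PFS analysis nor its power calculation uses the dosing days. Severity is minor and confidence is high.

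**What to change.** In Appendix D, footnote 13, replace Days 8-22 with Days 8-21. This alone removes the contradiction.

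In Section 6.4.2, add the end day for the biomarker cycle: capecitabine begins on Day 8 and continues through the evening of Day 21. It is best to state the morning start on Day 8 and the total (14 days, 28 doses) as well. Without them, a patient who starts in the evening of Day 8 and stops in the evening of Day 21 would take 1 + 13 × 2 = 27 doses, one short.

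The cost is a few words in two places at the next amendment. No design or analysis text needs to change.

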Appendix E. Laboratory Tests

CBC with differential		
• hematocrit	• WBC (total and differential)	• absolute neutrophil count
• hemoglobin	• red blood cell (RBC) count	• absolute lymphocyte count
• platelet count		
Chemistries with liver function tests (LFTs)		
• albumin	• blood urea nitrogen (BUN)	• potassium
• alkaline phosphatase (ALP)	• chloride	• sodium
• ALT	• creatinine	• total bilirubin
• AST	• glucose	• total protein
• Bicarbonate	• calcium	
Thyroid Function Tests		
• thyroid stimulating hormone (TSH)	• total triiodothyronine (T3)	• free tyroxine (T4)
Pregnancy Test		
• serum β -HCG pregnancy test
